the existing literature focuses on studies that have been conducted with patients having scheduled surgery and therefore administration of these drugs were standardized. Management of trauma patients on the other hand varies as patients present with varying injuries and requires individualized care plans. Accordingly, this study aims to reduce patients' consumption of narcotics in the hospital by utilizing multiple doses of adjunctive non-opioid analgesia for pain management in trauma patients.

Significance

The incidence of prescription opioid analgesic use has continued to increase and unfortunately the death rate from drug overdoses has shown a similar increase over the last several years. With alarming rates of drug-related deaths in West Virginia and the U.S. overall based on CDC data, it is crucial for clinicians to understand the impact that medical use of opioids may have on patients' mental and physical health. Especially, in the trauma patient population where opioid-based analgesia is commonly used to manage acute pain, it is important to treat the patient's pain without adding to the already growing problem. It is important for practitioners to be mindful and try to prescribe the lowest most effective dose needed to optimally control pain. Use of adjunctive analgesics may help lessen the amount of opioids prescribed and help the patient on their path of healing not just physically, but also emotionally and mentally.

Methodology

Study design

This will be a prospective, randomized trial with patients admitted to Charleston Area Medical Center's (CAMC) Trauma Services under the care of Nurse Practitioners (NPs) with attending supervision. Patients included in this study will be separated in three groups: Group A: Patients will be started on gabapentin upon admission after consented. They will receive 300 mg PO every 8 hours without dose titration. Group B: Patients will be started on pregabalin upon consent. They will receive 50 mg every 8 hours without dose titration. Group C: Patients in this group will be neither on gabapentin

nor pregabalin upon consent. In Groups A and B, patients with CrCl < 60mL/min will receive same dose given q12 hours. The q12 hour regimen may be increased to q8 hours if CrCl increases above 60mL/min during the 7 days study period or until discharge (if < 7 days post-enrollment).

Inclusion Criteria

1. NP service admissions
2. 18 year of age and older
3. Patients enrolled within 36 hours of admission

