4. Anticipated duration of hospitalization >24 hours from time of consent
5. Active order(s) for opioids in place at the time of enrollment

Exclusion Criteria

1. Clinician discretion based on patient care management
2. Intubated patients
3. Patients with epidural or peripheral nerve block
4. Patients with pregabalin/gabapentin as home medications
5. Patients receiving pregabalin/gabapentin upon admission
6. Traumatic brain injury patients
7. CrCl<30ml/min or on HD
8. Unable to take enteral medications
9. On Patient Controlled Analgesia (PCA)
10. Patients with complicated wound closure
11. History of epilepsy
12. Documented history of substance use disorder (this exclusion criterion was chosen to provide consistency among the study population as pain management may differ among these patients)

Setting

Charleston Area Medical Center's General Hospital, a Level 1 Trauma Center.

Sample Size

A sample size of 70 patient per study group which includes 10% attrition will be targeted (a total of 210 patients). This is based on Cohen's *d* formula with a significance of 0.05, 80% power and a medium effect size. Previous studies have evaluated the impact of single dose administration of pregabalin and gabapentin on pain and opioid consumption and were mostly conducted with patients having scheduled surgery. The current study, however, is designed to examine the effectiveness of multiple doses of these drugs in acutely injured trauma patients. Therefore, past reliable data could not be used for the power calculation for this study and Cohen's *d* coefficient was used for effect size. A medium effect size, which indicates a 69% difference between treatment and control groups was set by clinicians. For sample size estimation, instead of using effect size for the overall ANOVA which tests a general hypothesis we utilized effect sizes for the planned comparisons [(pregabalin vs. gabapentin); (pregabalin vs. neither pregabalin nor gabapentin); (gabapentin vs. neither pregabalin nor gabapentin)] using t-statistic.

Procedure/Protocols

Pre-intervention

- The clinical research coordinator will review the investigator's census on a daily basis in order to identify new admissions who may be study candidates.
- All patients who are eligible will be informed about the study. Patients with capacity who agree to participate will be consented using the consent form as written within 24 hours of admission. A note will be made in the patient's chart detailing the consent.

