- A randomization schedule will be generated using a SPSS algorithm. Patients will be assigned a study number and allocated to a respective study arm in order as they are consented.
- Both pregabalin and gabapentin are frequently used as adjunct analgesia in this patient population at CAMC. Thus, there will be no additional cost for participating in the study. However, blinding would not be in the best interest of the study because the design of these medications are identifiable to the trauma providers and it will be costly to get them blinded for this study. The patient will sign and date the consent and the HIPAA authorization form (which will be attached to the consent). Each patient will be assigned a patient study number and randomized accordingly to a pre-determined study arm.
- Original signed consent will be kept and stored in a binder at the CAMC Trauma Research Office. A copy of the consent form will be placed in the patient's chart and another will be given to the participant.

Intervention

- Patients in the pregabalin group will receive 50 mg q8 without dose titration. Patients in the gabapentin group will receive 300 mg q8 without dose titration. Patients enrolled with CrCl < 60mL/min will receive same dose given q12 hours.
- Adjunctive non-opioid analgesia, i.e. non-steroidal anti-inflammatory agents, may also be added at the managing service's discretion. Non-narcotic analgesia as adjunctive therapy may be added at the managing service's discretion. Total daily acetaminophen dose is not to exceed 3 gm.
- Following enrollment, the patients' opioid analgesia regimen may be increased or decreased at the managing service's discretion. Narcotic analgesic can be increased or decreased by 2.5 mgs of oxycodone or equivalent (i.e. oxycodone 5 mg q4 hrs as needed

to 7.5 mg oxycodone q4 hrs as needed) or increasing the dose of intravenous morphine by 2 mgs or equivalent.

- Decreasing dose of the opioids is at the discretion of the managing service.
- Patients with pre-existing narcotic use will be placed on their home regimens or an intravenous equivalent using a standardized dosing conversion table and adjustments can be made at the discretion of the managing service.

Data Collection

Data will be collected via patient chart review and institution's trauma registry. Data will be collected in an Excel spreadsheet. The following data will be collected for each patient:

- Demographics
 - Gender
 - Age
 - Height
 - Weight

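### No rule holds study drug if CrCl falls below 30 mL/min or haemodialysis (HD) starts after enrolment, and the dose after a later fall below 60 is unclear

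*Combined protocol and SAP*

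**What the plan says.** Renal function appears in four places in the combined protocol and SAP.

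- **Methodology, Study design.** "In Groups A and B, patients with CrCl < 60mL/min will receive same dose given q12 hours". The sentence names no time point. The next one allows a change during the study: "The q12 hour regimen may be increased to q8 hours if CrCl increases above 60mL/min during the 7 days study period".
- **Procedure/Protocols, Intervention.** The standard doses are fixed: "Patients in the pregabalin group will receive 50 mg q8 without dose titration" and "Patients in the gabapentin group will receive 300 mg q8 without dose titration". The renal rule follows: "Patients enrolled with CrCl < 60mL/min will receive same dose given q12 hours". This section does not repeat the upward step.
- **Exclusion Criteria, item 7.** "CrCl<30ml/min or on HD". This is an entry criterion only.
- **Data Collection.** Creatinine is recorded daily after enrolment, in a section that opens with "Data will be collected via patient chart review". No dosing action is attached to it.

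No section gives a rule to reduce, hold or stop study drug when renal function worsens after enrolment.

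**The concern.** The plan expects CrCl to move within the 7 days, because it provides for a rise above 60. It does not expressly provide for a fall, which is the direction that matters for safety.

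Two situations are left open. The first is a fall below 30 or a start of HD. The plan regards such a patient as unsuitable to enter, yet gives no instruction once the patient is in. The second is a fall below 60 in a patient on q8h, where two careful readers could arrive at different doses.

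What is at stake is dosing safety and consistent dosing within an arm. All patients have active opioid orders at entry (Inclusion Criteria, item 5), and Data Collection lists somnolence, dizziness and ataxia among the side effects to be recorded.

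**Working it through.** The plan states no figure on this point to reproduce. The check is a reading of the dosing rules plus simple arithmetic.

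**Inputs.** Unit doses are 300 mg gabapentin and 50 mg pregabalin. The standard interval is 8 hours and the renal interval 12 hours (Study design and Intervention).

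**Daily dose = unit dose × 24 / interval in hours.**

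- Gabapentin: 300 × 24/8 = 900 mg/day; 300 × 24/12 = 600 mg/day.
- Pregabalin: 50 × 24/8 = 150 mg/day; 50 × 24/12 = 100 mg/day.
- Ratio of q8h to q12h: 900/600 = 150/100 = 1.5, or one extra dose a day.

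**The two readings side by side** (gabapentin / pregabalin, mg/day):

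| Renal function | Study design sentence as a standing rule | Intervention sentence read literally |
|---|---|---|
| On q12h, CrCl rises above 60 | may go to 900 / 150 | not addressed |
| Enrolled at 60 or above, later falls below 60 but not below 30 | 600 / 100 | 900 / 150 |
| Enrolled at 60 or above, later falls below 30 or starts HD | 600 / 100 | 900 / 150 |
| Enrolled below 60, later falls below 30 or starts HD | 600 / 100 | 600 / 100 |
| Below 30 or on HD at entry | not enrolled | not enrolled |

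**Fall below 30 or new HD.** Neither column reaches zero. Even as a standing rule, the Study design sentence has no lower limit, so it gives q12h dosing however low CrCl goes. The smallest dose on any reading is therefore 600 mg/day gabapentin or 100 mg/day pregabalin. The same patient at entry would have received no study drug.

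**Fall below 60.** The columns differ only if the Intervention sentence is taken to apply q12h solely to those already below 60 at enrolment. On the other reading there is no excess. A cumulative excess would need the day of the fall, which the documents do not give, so none is stated.

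**Discretion.** The freedom that Intervention gives the managing service after enrolment covers opioids and adjunctive analgesics. Clinician discretion is also item 1 of the Exclusion Criteria, but there it governs entry. Neither is stated to cover holding or reducing study drug.

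**The case against.** The strongest reply is that usual care covers this. The trial is open-label, in inpatients at a Level 1 trauma centre, and "under the care of Nurse Practitioners (NPs) with attending supervision". The protocol describes both drugs as routine in this population, patients may withdraw at any time, and nothing forbids a clinician from stopping the drug. This stands as mitigation: many such patients would probably be managed sensibly. It does not fill the gap, because the protocol fixes the dose and does not say when a clinician should depart from it.

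A second reply is that entry exclusions need not become stopping rules. Intubation, PCA and nerve block are also exclusions without one. That is fair as a general point. The renal item differs because the plan ties the dose to CrCl and allows for CrCl to change during the study.

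A third reply concerns the stronger readings. A reader might infer that Study design and Intervention contradict each other. They do not: neither mentions a later fall, and the Intervention sentence may be only a shorter statement of the starting dose. A reader might also infer that the plan gives 50% too much drug to anyone who falls below 60. That holds only on the literal Intervention reading. Nor do the documents show that 600 or 100 mg/day is harmful below 30, since they give no safe limit there. These objections stand and bound the finding.

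**Conclusion.** The point holds as a dosing-safety gap of modest weight, worth correcting.

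- **Firm part.** There is no hold rule for CrCl below 30 or new HD. Followed as written, the plan keeps such a patient on at least 600 mg/day gabapentin or 100 mg/day pregabalin, at a level of renal function that it excludes at entry.
- **Conditional part.** A later fall below 60 is ambiguous. The figure of 1.5 times the q12h dose (900 instead of 600, or 150 instead of 100 mg/day) rests on the literal Intervention reading.

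The number of patients whose CrCl will fall is not given, so no frequency is claimed. A reader might take this further and infer a threat to the trial's result. The documents do not support that: nothing here changes the sample size, power, alpha or the primary comparison.

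**What to change.** Use the same paragraph under Study design and under Intervention, after the starting-dose rule:

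> Study drug is reduced to q12h if CrCl falls below 60 mL/min during the study period and held if CrCl falls below 30 mL/min or HD starts. It may resume at q12h when CrCl is again 30 mL/min or above off HD. The q12h regimen may be increased to q8h if CrCl rises above 60 mL/min.

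The increase stays optional, as now. Assign an existing study or clinical role to calculate CrCl each day and act on it. Age, weight, gender and daily creatinine are already collected, so no new data field is needed.

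The cost is a wording amendment, a small daily duty and slightly less study drug in a few patients. The creatinine must be read on the day rather than at later chart review. The plan records a daily value but does not say that the study orders the panel. If it is not drawn daily in routine care, it would have to be ordered for patients on study drug.

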- III. To assess effectiveness of pain control in each arm based on the average Numeric Pain Rating Scale score per 24 hours following randomization. This scale is a 10 point numeric scale that ranges from 0 that represents "no pain" to 10 which indicates the "worst pain imaginable."
- IV. To evaluate the differences among the study arms with respect to hospital length of stay and unplanned ICU admissions.

Background

According to the Centers for Disease Control and Prevention, trauma is the fourth leading cause of death in the United States.¹ It is a major cause of mortality throughout the world. There are many factors that can affect morbidity and mortality in trauma patients including pain. Trauma introduces acute as well as chronic pain into the lives of its victims.² In a study by Gross and Amsler, severity of pain before and at least 2 years after poly-trauma, which was defined as patients with a well-defined injury of at least two body regions, was evaluated. After 2.7 ± 0.9 years following injury, only 54% of poly-trauma patients were fully rehabilitated. An astonishing 59% had to undergo a change in their occupation due to their injury(s). In addition, 2 years post-trauma 85% of these patients continued to experience pain.³ Literature suggest that 22% of the population experience chronic pain and more than one third of those cases are the result of trauma. Forty-six percent of long-term survivors of high energy trauma report daily pain after their trauma as compared to only 5% before the accident.²

Improved pain management in trauma patients leads to increased comfort as well as reduced morbidity and improved long-term outcomes.⁴ Successful approaches for achieving adequate pain control can vary greatly from patient to patient resulting in difficulty with the routine provision of analgesia. Pain in trauma patients can be a complicated process. Injury severity is often related to the level of pain experienced by trauma patients; however, pain alone can complicate a patient's condition and potentially lead to further clinical deterioration of the patient. Baseline physiology of trauma patients can widely vary from young athletes to elderly frail adults. Presenting with multiple injuries, substance use disorder, delayed care, as well as psychological and emotional issues can further complicate the care process. Understanding pain in trauma patients and how to manage it is crucial to their care.

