 - Date & time of hospital admission and discharge
 - Comorbidities
- Urine and drug screen
- Admitting injury list
- Length of Stay
- Pre-existing (home) analgesic regimens
- Prior exposure of pregabalin or gabapentin
- Surgery dates and surgeries performed
- Inpatient analgesic exposure prior to enrollment (medications, dose, # of doses) and 7 days post-enrollment or until discharge (if < 7 days post-enrollment)

- Initial Incentive Spirometry value and 7 days post enrollment or until discharge (if < 7 days post-enrollment)
- Documented pain scores for each 24-hour period post-enrollment for 7 days or until discharge (if < 7 days post-enrollment)
 - Additional notation will be made to indicate the first pain score that coincides with the initiation of study medication
- Post-enrollment complications (unplanned intubation, unplanned ICU admission, incidence of VTE, infection, pneumothorax requiring chest tube placement, other)
- Post enrollment daily creatinine value from Basic Metabolic Panel
- Side effects including somnolence, dizziness, fatigue, ataxia, tremor, amnesia and others

Data Analysis

Descriptive analysis will be conducted for each variable in this study. Means and standard deviations or medians and interquartile ranges for continuous variables will be reported. For categorical variables, proportions and frequencies will be computed. To assess statistically significant difference between two cohorts, t-tests or Mann-Whitney U will be conducted for continuous variables. Categorical variables will be compared using chi-square or Fisher's Exact test. Outcome variables will be analyzed with ANCOVA or binary logistic regression controlling for differences in patient characteristics. A sub-analysis will be conducted by examining outcomes based on the number of days patients stay in the hospital post-enrollment. All comparisons will be performed at a level of significance of $p \leq 0.05$. Analysis will be done using 22.0SPSS version.

Subject Population

There are no known vulnerable participants to be included (specifically those under 18, prisoners, or those with pre-existing cognitive defects).

Benefits

Our study might show that pregabalin and gabapentin as adjunctive non-opioid analgesia may significantly reduce opioid usage in trauma patients, which will perhaps lessen complications related to use of opioids in trauma patients.

Risks and Discomfort

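### No pre-randomization pain score is collected in any arm, so the Objective III analysis cannot adjust for starting pain; the cost is precision, not bias

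*Combined protocol and SAP*

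**What the plan says.** All references are to the combined protocol and SAP.

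- **Pain endpoint.** Secondary Objective III compares arms on the "average Numeric Pain Rating Scale score per 24 hours following randomization". It is a post-randomization average, not a change from baseline.
- **Pain data.** Data Collection lists "Documented pain scores for each 24-hour period post-enrollment for 7 days" or until earlier discharge. A sub-item adds a notation for the "first pain score that coincides with the initiation of study medication".
- **Other starting values.** The same list takes "Inpatient analgesic exposure prior to enrollment (medications, dose, # of doses" and so on, and an initial incentive spirometry value.
- **Allocation.** Under Pre-intervention, patients are "allocated to a respective study arm in order as they are consented". Study design describes the third arm thus: "Group C: Patients in this group will be neither on gabapentin" nor on pregabalin.
- **Analysis.** Data Analysis plans ANCOVA or logistic regression for the outcomes, adjusting for differences in patient characteristics. It names no covariates.
- **Source and timing.** Data come from chart review and the trauma registry. The Inclusion Criteria allow enrollment up to 36 hours after admission and require an active opioid order.

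**The concern.** Pain is measured repeatedly as an efficacy outcome, but the list gives it no starting value. Analgesic exposure, by contrast, is taken on both sides of enrollment. The Background says that pain relates to injury severity and that patients' baseline physiology varies widely, so differences in starting pain between patients are to be expected.

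The flagged score does not fill the gap. It is tied to an event that happens only in two arms, after the arm is known, in an open-label trial. Anyone following the list exactly would reach the analysis with no common pre-randomization pain value. The ANCOVA could then not use the covariate closest to the Objective III outcome, and the baseline table could not show whether the arms started with similar pain.

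**Working it through.** **1. Is there a baseline anywhere?**

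| Score | Groups A and B | Group C |
|---|---|---|
| Before enrollment | not listed | not listed |
| At start of study medication | listed, after allocation | no such event |
| By 24-hour period after enrollment | listed | listed |

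No objective and no analysis sentence supplies a pre-randomization score. The documents do not say whether enrollment means consent or randomization. Even if a score were charted between the two, nothing designates it as a baseline.

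**2. The plan's own sample size.** Sample Size gives 70 per group including 10% attrition, at significance 0.05, 80% power and a medium effect. Taking medium as d = 0.5 and the test as two-sided (both assumptions), the normal approximation gives:

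n = 2 × (1.96 + 0.84)² / 0.5² = 2 × 7.84 / 0.25 = 62.7, so 63 per arm; 63 / 0.9 = 70.

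The figure reproduces, and nothing here disputes it. It supplies 63 evaluable patients per arm for the steps below.

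**3. Precision from adjusting for starting pain.** Let r be the correlation between the pre-randomization score and the 24-hour average. The documents give no value, so 0.2 to 0.6 is assumed. Relative to no adjustment, residual variance is multiplied by 1 − r² and interval width by √(1 − r²). The equivalent unadjusted sample is 63 / (1 − r²) per arm.

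| r | 1 − r² | Variance removed | √(1 − r²) | CI narrower by | Equivalent n per arm |
|---|---|---|---|---|---|
| 0.2 | 0.96 | 4% | 0.980 | 2% | 66 |
| 0.3 | 0.91 | 9% | 0.954 | 5% | 69 |
| 0.4 | 0.84 | 16% | 0.917 | 8% | 75 |
| 0.5 | 0.75 | 25% | 0.866 | 13% | 84 |
| 0.6 | 0.64 | 36% | 0.800 | 20% | 98 |

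**4. These are gains over an unadjusted analysis.** The plan already intends ANCOVA, and its data list includes injuries, surgeries and prior analgesic exposure. Against such a model, the r that counts is the partial correlation given those covariates. That is normally smaller, so the gain is smaller too. The documents do not allow it to be estimated.

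**5. Chance imbalance is not a further loss.** The standard error of the difference in starting pain between two arms is √(2/63) = 0.178 SD, with 95% limits of about ±0.35 SD. That is the size of imbalance the baseline table could not reveal. The unadjusted standard error of the pain contrast already contains its effect. In SD² units, the variance 2/63 = 0.0317 splits at r = 0.5 into 0.75 × 0.0317 = 0.0238 that remains after adjustment and 0.25 × 0.0317 = 0.0079 attributable to starting pain. The second part is the 25% shown in the table.

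**The case against.** **Pain is secondary, and the primary outcome has its own starting data.** This stands. Opioid use is the primary outcome, and pre-enrollment exposure and home analgesics are collected. The point is confined to Objective III.

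**Randomization protects the comparison.** This also stands. A reader might infer that a drug effect could not be told apart from a chance difference in starting pain. The documents do not support that: the arms are randomized, the contrast is unbiased, and its standard error allows for chance imbalance (step 5).

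**The first-dose score might be used as a baseline.** A reader might infer this from the notation. No section says so, and Objective III is not defined as a change from baseline. The misuse is hypothetical; it is enough that the notation cannot serve as a baseline in Group C.

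**The correlation may be low.** Opioid doses may be changed at the managing service's discretion, which could weaken the link between early and later pain. For this reason the range starts at 0.2, where the gain is only 2% of interval width.

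**Nothing is lost for good.** This is largely right. The data come from charts, so the score can probably still be retrieved. The gap is in the abstraction list, not necessarily in the source. That makes the change cheap, but a list followed as written still leaves the covariate out.

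**Conclusion.** The point holds as a modest, inexpensive improvement to a secondary analysis. The planned dataset has no pre-randomization pain score in any arm, and the flagged score cannot stand in for one. As a result, starting pain can be neither adjusted for nor described by arm.

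Under the assumed correlations, the loss is 2% to 20% of interval width relative to an unadjusted analysis, and less relative to an ANCOVA on the other listed covariates. It is not evidence of bias in Objective III, and it does not affect the sample size or the validity of the primary comparison.

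**What to change.** - In Data Collection, add for all three groups the last charted numeric pain score before randomization, the time of that score, and the time of randomization. The list now names times only for admission and discharge, so the randomization time is needed to establish that a score came first.
- In Data Analysis, name this score as a covariate in the Objective III ANCOVA, and report it by arm in the baseline table.
- State that the first-dose notation is descriptive only.
- State in advance how patients with no charted pre-randomization score stay in the analysis.

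One score is enough. A mean over all scores since admission would take more abstraction and has no use in this analysis.

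The cost is a few more fields from a chart already under review and a few sentences of text, with no patient contact and no extra patients. The downside is that some patients may have no charted score before randomization, which would reduce the gain.

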Pregabalin vs. Gabapentin on Reducing Opioid Usage in Trauma Patients

NCT# 04705480

Protocol

IRB Approval Date: 07/22/2024

Title: Pregabalin vs. Gabapentin on Reducing Opioid Usage in Trauma Patients

Abstract

The pain following trauma can be difficult to manage because it can have more than one cause and differ from patient to patient. It is not uncommon for trauma patients to have localized pain related to their injuries coupled with a component of nerve pain. Pregabalin and gabapentin have both been effectively used in many studies to reduce opioid pain medication usage in patient care. Gabapentinoids (pregabalin and gabapentin) have historically been used to treat seizures, nerve pain, and anxiety. Current research, however, has successfully shown their effectiveness as pre- and post-operative pain medications. However, these studies have examined single-dose use of pregabalin/gabapentin in the management of postoperative pain and opioid consumption. As of yet, studies have not investigated the efficacy of multiple-dose administrations of these drugs on opioid consumption. The purpose of this study is to test the effectiveness of using multiple doses of pregabalin or gabapentin in combination with traditional opioid pain medications in order to decrease the amount of opioid pain medication usage in trauma patients. The primary outcome is to compare those receiving multiple doses of pregabalin vs. gabapentin vs. those receiving neither, and to determine daily average opioid requirement at 24 hour increments up to 7 days following initiation of study medication.

Word Count-163

Aims/Objectives

Primary Objective:

To determine if adding multiple doses of pregabalin or gabapentin upon admission will reduce opioid usage in trauma patients in the first 7 days of hospitalization or until discharge, if discharge < 7 days post-enrollment.

Secondary Objectives:

- I. To compare the change in documented incentive spirometry values from morning physical assessment among patients in each of the study groups who have at least 1 rib fracture. Decreased pain scores may correlate with improved incentive spirometry values, which may facilitate recovery from lung-related injury.
- II. To compare the proportion of patients requiring intubation among the study groups. Worsened pain is associated with respiratory distress which increases likelihood of intubation.

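### The planned sub-analysis by post-enrollment days in hospital groups patients on a post-randomization variable and should be descriptive, without p-values

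*Combined protocol and SAP*

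**What the plan says.** The combined protocol and SAP, Data Analysis, plans: "A sub-analysis will be conducted by examining outcomes based on the number of days patients stay in the hospital post-enrollment". It defines no stay groups, names no model and does not say whether the result is descriptive. The sentence before it gives the general method: "Outcome variables will be analyzed with ANCOVA or binary logistic regression controlling for differences in patient characteristics". The covariates are not named. The sentence after it begins "All comparisons will be performed at a level of significance" and gives 0.05 as the threshold.

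Three other places bear on this:

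- **Secondary Objectives, item IV:** "To evaluate the differences among the study arms with respect to hospital length of stay and unplanned ICU admissions". Stay is therefore itself an outcome compared between arms.
- **Procedure/Protocols, Pre-intervention:** patients are allocated as they consent, and the trial is not blinded. Days after enrollment accrue after allocation, and discharge is decided by staff who can know the arm.
- **Primary Objective:** opioid use is studied "in the first 7 days of hospitalization or until discharge, if discharge < 7 days post-enrollment". The Abstract describes the outcome as "daily average opioid requirement at 24 hour increments up to 7 days following initiation of study medication".

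**The concern.** Randomization makes the arms comparable as whole groups. It does not make them comparable within groups formed by something that happens later and that treatment may influence.

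Suppose a drug speeds discharge and sicker patients both stay longer and need more opioid. A treated patient who stays four days is then, on average, sicker than a control patient who stays four days, because the same patient without the drug would have stayed longer. The treated arm shows higher opioid use in that stay group even if the drug does nothing to opioid use. Part of a true opioid-sparing effect could be hidden, or extra use suggested where there is none. If the drug lengthens stay, the error reverses.

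Because the 0.05 rule follows directly, p-values from such a split could be read as supporting or contradicting the primary result.

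**Working it through.** **The plan's own figure.** For a medium effect (taken as d = 0.5), two-sided 0.05 and 80% power, n = 2(1.960 + 0.842)²/0.5² = 62.8, so 63 per arm; 63/0.90 = 70. The stated 70 per group reproduces. No stated figure is in error, and 63 evaluable per arm is used below.

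**Assumptions, none from the documents.** Log stay and log opioid use each have SD 0.5 and correlate ρ = 0.42 through severity. Mean control stay is 5.10 days, with a minimum of 24 h. Use falls 15% per day. The drug has no effect on use and lowers log stay by δ = 0.05, 0.1 or 0.2. Mean stay becomes 5.10 × exp(−δ) = 4.85, 4.61 or 4.18 days, which is 0.25, 0.5 or 0.9 day shorter.

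**Size of the false difference.** At a fixed observed stay, treated patients would have had a log stay δ longer without the drug. Their log use is therefore higher by ρ × (0.5/0.5) × δ, and the false excess is exp(ρδ) − 1. The simulation used 1,000,000 patients per arm and one-day groups from 2 to 7 days.

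| Case | δ = 0.05 | δ = 0.1 | δ = 0.2 |
|---|---|---|---|
| Formula, ρ = 0.42 | 2.1% | 4.3% | 8.8% |
| Simulation, ρ = 0.42 | 1.9-2.2% | 3.9-4.6% | 8.3-8.9% |
| Simulation, ρ = 0.21 | 0.7-1.5% | 1.7-2.4% | 3.9-4.7% |
| Simulation, ρ = 0.72 | 3.5-3.8% | 6.6-7.4% | 14.0-16.0% |

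At δ = 0 the formula gives exp(0) − 1 = 0: no change in stay, no bias.

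**With ANCOVA.** Take one baseline covariate with correlation c to severity, and let severity load equally on stay and use. The slope ρ is then replaced by ρ(1 − c²)/(1 − ρc²).

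- c = 0.5: slope 0.352; excess 1.8, 3.6, 7.3% (simulated 1.6-1.9, 3.3-3.9, 6.9-7.5%).
- c = 0.7: slope 0.270; excess 1.4, 2.7, 5.5% (simulated 1.2-1.6, 2.4-3.0, 5.3-5.9%).
- c = 0.8: slope 0.207; excess 1.0, 2.1, 4.2% (simulated 0.9-1.2, 1.9-2.2, 4.0-4.5%).

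Even c = 0.8 leaves about half the bias (0.207/0.42 = 0.49).

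**False positives with 63 per arm** (2,000 simulated trials, unadjusted t-tests on log average use, ρ = 0.42):

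| Analysis | δ = 0.05 | δ = 0.1 | δ = 0.2 |
|---|---|---|---|
| One-day groups (about 3-17 per arm) | 5.2% | 5.6% | 6.5% |
| Two groups split at 4 days | 4.5-5.6% | 5.9-6.4% | 8.2-9.9% |
| Stay as a factor | 6.2% | 8.1% | 16.1% |

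The last row can be checked by hand. Bias over standard error is 0.023/0.083 = 0.28, 0.041/0.083 = 0.49 and 0.081/0.085 = 0.95. Putting k for this ratio into Φ(−1.96 + k) + Φ(−1.96 − k) gives 5.9, 7.8 and 15.9%. Independent reruns put this row at about 5-6, 7-8 and 15-16%. With stay unchanged, rejection is about 5%.

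**A second model** splits at the median stay. A shift in stay of 0.25 SD gives 5-8% rejection per group for correlations 0.3-0.7, and a shift of 0.5 SD gives 7-17%. The comparison of all patients stays at about 5%.

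**All randomized patients to discharge or day 7.** In the first model the average moves +1.1, +2.3 and +4.8%, because early high-use days weigh more when the window is shorter. A rerun of 3,000 trials rejects about 6, 6 and 9%. This is a real difference in average in-hospital use, not a loss of comparability.

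**The case against.** The strongest reply is that the text says only that outcomes will be examined by days of stay. It does not state that arms will be tested within stay groups or that stay will enter a model. The section opens with descriptive analysis, and the sentence may be meant as a check on unequal observation windows. This stands in part: testing is the natural reading next to the 0.05 rule, not an explicit commitment. If the intent is descriptive, saying so costs nothing.

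Second, nothing in the documents shows that treatment changes stay. Objective IV asks the question and does not answer it. This also stands, and it is why the point is conditional.

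Third, the effect is small in most cases. The 16% needs both the largest shift and stay entered as a factor, and it is unadjusted although adjustment is planned. That is correct, but with no covariates named there is no assurance that severity is captured.

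A reader might go further and infer that intubation ("To compare the proportion of patients requiring intubation among the study groups") and unplanned ICU admission are split by their own consequence, since either could lengthen stay. This is plausible, but the documents give no figure for it and it is not needed for the point.

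**Conclusion.** The point holds as a conditional weakness in one sub-analysis. Arm comparisons by post-enrollment stay lack the protection of randomization if treatment alters stay and severity drives both stay and opioid use. Under the assumptions above, the false excess is about 2, 4 or 8-9% unadjusted, and smaller with a good severity covariate. The false-positive rate is close to nominal except at the largest shift, where it is about 8-10% in a two-group split and 15-16% with stay as a factor. Size and direction in this trial are unknown.

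Two stronger readings are not supported. A reader might infer that the primary comparison is biased. The Background gives the aim as reducing "consumption of narcotics in the hospital by utilizing multiple doses of adjunctive non-opioid analgesia", and a comparison of all randomized patients to day 7 or discharge answers that question without this selection, though over windows of unequal length.

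A reader might also infer that the later 24-hour increments should become descriptive. Increments limited to patients still in hospital do share the mechanism (about +1, +3 and +7% on day 7 in the same illustration). But they belong to the stated primary outcome, and giving up their testing is a separate trade-off that this sub-analysis sentence does not force.

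**What to change.** Do not test arms within length-of-stay groups. Replace the sub-analysis sentence in Data Analysis with:

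> Outcomes by post-enrollment days in hospital will be summarized by arm without p-values and not interpreted as treatment effects, because stay is measured after randomization.

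The cost is one tested sub-analysis. The change is to wording only, with the same data and software. The primary outcome and its 24-hour increments need no change.

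Three additions are optional and not required by this point: a comparison over the first 24 or 48 h in all randomized patients, per hour observed; a longitudinal mixed model with its assumptions stated; and subgroups on baseline features already collected, such as the injury list or home analgesic regimen.
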